**Study start date (actual)**

2020-12-01

### **Study completion date (anticipated)**

2025-12-01 (All outcomes of the last patient are recorded 3 years postoperatively, death or loss to follow-up of the last patient.)

### **Primary outcomes**

[figure not shown]
- The degree of Angle denotes the degree of angle between the linear stapler and the longitudinal axis of the rectum when transecting the distal rectum.
- The degree of  $\Delta$ Angle represents the degree of angle between the simulated stapling line with the total mesorectal excision approach and the real stapling line with the transanterior obturator nerve gateway approach (this outcome is measured only in patients of the experimental group).
- Length of distal resection margin indicates the shortest distance between the distal border of the tumor and the edge of the distal resection.
- Rate of conversion to transanal transection and anastomosis of the rectum: For each case, whether there is a conversion to transanal transection and anastomosis of the rectum during the operation will be recorded. The gross conversion rate (No. of cases undergoing conversion/total No. of cases enrolled \*100%) for each group will be calculated immediately after the last patient's surgery.
- Rate of anastomotic leakage: Whether the patient complicates with anastomotic leakage postoperatively will be followed up till 6 months after surgery. The gross anastomotic leakage rate (No. of cases diagnosed with anastomotic leakage/total No. of cases enrolled \*100%) for each group will be calculated 6 months after the last patient's surgery. Anastomotic leakage will be diagnosed if the patient has clinically apparent leakage signs (such as the emission of gas, pus, or feces from the pelvic drain, or peritonitis) or extravasation of endoluminally administered watersoluble contrast medium according to CT.

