To solve the problem above, on the basis of a large number of ISR-DST performing experience, [name], the director of this clinical trial has explored a new distal rectal resection method-- transanterior obturator nerve gateway approach. This approach can conspicuously expand the pelvic space and optimize the dissection angle without significantly prolonging the operative time, thus reducing the technical difficulty. So, by using this method, it would be more likely to preserve the anus and reduce the possibility of converting to transanal approach without breach of tumor's radical resection. The purpose of this clinical trial is to prospectively collect and compare data on the patients' perioperative items and postoperative functional and oncological outcomes of this novel approach with the traditional approach, so as to confirm the safety and feasibility of this novel approach and its advantages over the traditional approach.

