- 4) Urethral catheterization will be routinely done preoperatively
- 5) If the patient refuses to accept the novel approach before surgery, they will be directly enrolled in the traditional group. If both approaches are acceptable to the patient, the decision whether to use the novel approach will be made according to the intraoperative

conditions (see operating procedures below).

- Operating procedures

General anesthesia; Modified lithotomy position (Fig. 1a); Establishment of pneumoperitoneum: Place a trocar 1cm above the umbilicus through which to establish pneumoperitoneum and keep the abdominal pressure as 12 mmHg (millimeters of mercury).

Trocar placement: above the umbilicus (trocar C, 10 mm), upper right and left quadrants (trocars B and D, 5 mm), lower right quadrant (trocar A, 12 mm), lower left quadrant (trocar E, 5 mm), the midpoint between the pubic symphysis and umbilicus (trocar F, 5 mm).

[figure not shown]

Fig.1 Patient position and trocar placement

Abdominal exploration: Explore the abdominal cavity in accordance with the principle of non-contact, from far to near step by step, explore the tumor finally.

The mesosigmoid and mesorectum are dissected from the right lateral rectum towards the root of the inferior mesenteric artery (IMA). The IMA is transected and ligated, so is the inferior mesenteric vein. Posterior space of the descending colon is dissected following opening the peritoneum beside the left rectum. The rectum in the pelvis is mobilized from posterior rectal space, anterior rectal space to bilateral rectal space successively. The lower edge of the tumor is marked by a clamp. The linear stapler is placed in the pelvis to clamp the distal rectum below the tumor to see if the transection can be done more than 1cm from the lower edge of the tumor. If yes, the distal rectum will be transected by the traditional approach (that means the patient will be assigned to the traditional group). The proximal bowel is transected through a small midline incision. Then the coloanal

anastomosis will be done intracorporeally. A surgical drain is placed in the pelvis and a terminal ileostomy is routinely performed. All incisions are closed.

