If the distal rectal transection cannot be done more than 1cm from the lower edge of the tumor, the anterior obturator nerve gateway approach will be used (that means the patient will be assigned to the experimental group). The steps are as follows: The peritoneum covering the ureter and external iliac artery is opened more than 2 cm across the vas deferens (male) or round ligament (female). The Retzius space and vesicohypogastric fascia are exposed. The obturator vessels and obturator nerve are properly identified. Care should be taken to avoid any injury when using energy devices near the obturator nerve. The gateway is then opened through the TME (total mesorectal excision) compartment and the lateral compartment. If necessary, an “endoloop” can be placed through the gateway, and the bundled S2-4 nerves, ureter and bladder vessels are gently retracted toward the cranial direction to widen the gap. The linear stapler is placed in the gateway to vertically transect the distal rectum. The following procedures are the same with the traditional group as described above.

During the operation, the following variables will be recorded: the angle between the linear stapler and the rectum, distance from the lower edge to the resecting margin, whether the operation converted to transanal approach, operative time, bleeding volume, anastomotic height from anal verge and the length of the stapling line.

➤ **Postoperative management:**

The following information will be recorded:

1) Vital signs (body temperature, pulse rate, respiration rate, blood pressure) are routinely monitored, gross volume of fluid input and output will be recorded every 24h, blood routine, the comprehensive metabolic panel and coagulation function tests will be performed every 3 days.

2) The time of catheter removal (days after operation), residual urine volume in the bladder will be measured by ultrasound examination. Whether there is a request to be re-catheterized or take oral medication to relieve the dysuria. All patients will be asked to fulfil the IPSS (International prostate symptom score) questionnaire to assess urinary function.

**Table 1.** International prostate symptom score assessing urinary function

In the past month:	Not at All	Less than 1 in 5	Less than Half the	About Half the	More than Half	Almost Always
--------------------	------------	------------------	--------------------	----------------	----------------	---------------

		Times	Time	Time	the Time	

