### **Statistics**

IBM SPSS (Statistical Package for the Social Sciences) Statistics 25 (IBM, Inc., Armonk, NY) will be used to perform statistical analyses. The *t* test and Mann-Whitney *U* test were used for quantitative data between groups. Qualitative data were compared by  $\chi^2$  or

Fisher's exact test and survival distributions were analyzed by log-rank test.

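### Does ΔAngle, a primary outcome measured in one group only, need an analysis that the Statistics section does not name?

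*Combined protocol and SAP*

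**What the plan says.** Primary outcomes defines ΔAngle as "the degree of angle between the simulated stapling line with the total mesorectal excision approach and the real stapling line" obtained with the gateway approach, and adds that "this outcome is measured only in patients of the experimental group". The visible text gives no sign or direction. A figure belongs to this section but is not reproduced in the copy reviewed. The other four primary outcomes (Angle, distal margin length, conversion rate and leakage rate) carry no such restriction.

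Statistics is short. For measured data it names the t test and the Mann-Whitney U, and the sentence ends "test were used for quantitative data between groups". Proportions go to chi-square or Fisher's exact test and survival to the log-rank test. No mean, SD or confidence interval is specified for any outcome. The document states no significance level and no success rule.

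The Treatment section, under operating procedures, explains how the groups arise. First, "The linear stapler is placed in the pelvis to clamp the distal rectum below the tumor". If a margin of more than 1 cm is attainable, the text continues "If yes, the distal rectum will be transected by the traditional approach". The gateway is used "If the distal rectal transection cannot be done more than 1cm from the lower edge of the tumor". Item 5 of the preoperative preparation also sends patients who decline the new approach to the traditional group. Sample size plans 100 experimental patients and at least 100 controls.

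**The concern.** Set side by side, the two sections do not meet. ΔAngle has no control values, so neither the two-sample t test nor the Mann-Whitney test can be run on it, and the other named tests are for other kinds of data. On a literal reading, one of five primary outcomes has no planned analysis.

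This outcome also matters more than its place in the list suggests. Willing patients are grouped by how difficult the transection proves at the test clamp, so a between-group comparison of Angle mixes the approach with anatomy. ΔAngle compares two lines in the same patient and speaks directly to the Background claim that "This approach can conspicuously expand the pelvic space and optimize the dissection angle".

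There is a trap as well. If an analyst filled the gap with a one-sample test against zero, and ΔAngle were recorded as a plain angle that cannot be negative, the test would be significant whether or not the gateway changed anything.

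**Working it through.** **Plan's own figure.** No number is stated for ΔAngle, and the sample size has no stated inputs, so there is nothing to reproduce. The only input taken from the document is n = 100 at most (Sample size). All SDs below are assumptions.

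**1. Does a named test apply?** A two-group test needs values in both groups. ΔAngle has up to 100 experimental values and no control values. No named test applies, so the textual point is right.

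**2. What would a plain summary deliver?** The 95% half-width is t(0.975, 99) × SD/√100 = 0.198 × SD. For an SD of 5, 10 or 15 degrees this is 0.99, 1.98 or 2.98 degrees. A mean with its interval is informative without any test.

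**3. How bad would a test of the unsigned value be?** Suppose there is no true change and the errors are normal. The absolute value then has mean σ√(2/π) = 0.798σ and SD σ√(1 − 2/π) = 0.603σ. The ratio is 1.324 whatever σ is, so t ≈ 1.324 × √100 = 13.2. In simulation (5,000 trials for each SD of 5, 10, 15 and 20 degrees, n = 100, two-sided 5%), the unsigned version rejected in 100% of trials and the signed version in 4.7% to 5.9%.

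**4. How far would the unsigned mean itself be off?** Let the true change be D and the reading error SD be s per line, independent, so σ = s√2. The expected unsigned value is

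σ√(2/π)·exp(−D²/2σ²) + D·[1 − 2Φ(−D/σ)].

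| True change (degrees) | s = 3 | s = 5 | s = 10 |
|---|---|---|---|
| 0 | 3.39 | 5.64 | 11.28 |
| 5 | 5.50 | 7.00 | 11.98 |
| 10 | 10.03 | 10.50 | 13.99 |
| 20 | 20.00 | 20.01 | 21.01 |
| 30 | 30.00 | 30.00 | 30.17 |

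The bias is material only when the change is small relative to reading error. At 20 degrees it is 21.01 − 20 = 1.01 at worst, and at 30 degrees it is 0.17 at worst. The operating procedures aim for a near-perpendicular cut: "The linear stapler is placed in the gateway to vertically transect the distal rectum". If the real line is at 90 degrees, any true difference must be a move toward perpendicular, so a sign adds nothing.

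**5. Would a simple sign rule improve matters?** Take real minus simulated, with readings past 90 kept. A move from 85 to 100 scores +15, yet the distance from perpendicular grows from 5 to 10. A move from 100 to 90 scores −10, yet the distance falls from 10 to 0. A plain signed difference can therefore point the wrong way. A sign written in without sight of the figure could also contradict a convention the figure already sets.

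**The case for a change.** The strongest case for a change is that a primary outcome should not depend on the analyst's good sense. ΔAngle is the primary outcome least exposed to the allocation rule. Recruitment began on 2020-12-01, before the protocol date of 2021/9/7, so an analysis chosen later would be harder to defend. One sentence would settle it at almost no cost.

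Part of this stands. No named test fits, and the within-patient comparison is the more credible evidence on angle. A reader of the eventual report should expect the mean, SD, confidence interval and number of patients with ΔAngle available, and should discount a p-value against zero if the quantity was recorded unsigned.

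The rest is weaker. By restricting ΔAngle to one group, the protocol already shows that no group comparison is intended, and a within-group description is the natural reading. The missing summary is not peculiar to ΔAngle, since Statistics specifies none for any outcome. The false-positive result belongs to a test that appears nowhere in the plan. Whether direction is undefined cannot be judged without the figure.

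**Conclusion.** No change follows. The gap is real but is one of missing detail that analysts fill sensibly: up to 100 within-patient values, summarised by a mean and SD with an interval of about ±0.2 SD. No rule that the plan does state gives a wrong result, and no sample size or success criterion depends on ΔAngle. A purely descriptive treatment is acceptable.

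The alarming figure, t of about 13 with no true change, is correct for an unsigned value tested against zero, but that test is hypothetical. Bias in the unsigned mean is about 1 degree or less from a true change of 20 degrees up, assuming independent normal errors of 3 to 10 degrees per line and lines in one plane. For changes of 10 degrees or less with large reading error the bias would be noticeable, up to 11.28 degrees at no change with s = 10. That bears on how the result is read. The other four primary outcomes are unaffected because between-group tests can be applied to them.

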### **Statistics**

IBM SPSS (Statistical Package for the Social Sciences) Statistics 25 (IBM, Inc., Armonk, NY) will be used to perform statistical analyses. The *t* test and Mann-Whitney *U* test were used for quantitative data between groups. Qualitative data were compared by  $\chi^2$  or

Fisher's exact test and survival distributions were analyzed by log-rank test.

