## **Methodology**

Prospective, Non-randomized, Interventional, Controlled

*The Biomedical Research Ethics Committee of Peking University First Hospital* is overseeing the research. ([contact]; Email: [[contact]](mailto:[contact]); Address: [name])

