### ➤ Exclusion criteria

- 1) The patient had previous abdominal surgery that will significantly infect the laparoscopic procedures;
- 2) Patients requiring emergency surgery owing to intestinal obstruction, perforation, or uncontrolled bleeding caused by tumor;
- 3) Patients with poor anal function preoperatively (Wexner score  $\geq 10$ );
- 4) ASA (American Society of Anesthesiologists) grading  $\geq IV$ ;
- 5) Pregnant patients;
- 6) Patients concomitant with severe mental illness;
- 7) The patient or the patient-authorized representative can't understand the contents and objectives of the study.

➤ **Withdraw criteria**

- 1) ISR cannot be performed by intraoperative evaluation and is replaced by Miles surgery;
- 2) Distant metastasis is confirmed intraoperatively or by postoperative pathological findings;
- 3) Patients had other primary tumors requiring surgical/drug treatment during the study, or had other illnesses that prevent the patient from continuing to participate this study;
- 4) Patients decide to withdraw from the study for any reason, or who are unable to complete the study because of any objective reasons.

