### **Treatment**

If the participant matches with the requirements for this study and agrees to take part in it, once hospitalized, the participant will complete the established preoperative tests including blood routine, the comprehensive metabolic panel, blood coagulation function, tumor markers, blood type, infectious disease screening tests, chest, abdominal and pelvic CT (Computed Tomography) scan and MRI, colonoscopy, echocardiogram, pulmonary function, venous duplex ultrasound of legs. All male patients will be routinely asked to fill

in the IIEF-5 sexual function scoring questionnaire preoperatively.

The following comprehensive treatment will be depended on the examination results:

➤ **Neoadjuvant therapy**

The treatment plan will be made in accordance with the NCCN (National Comprehensive Cancer Network) Guidelines for Diagnosis and Treatment of Colorectal Cancer (Version 1.2021).

Neoadjuvant chemoradiotherapy: Pelvis radiotherapy with a total dose of 50 Gy with 25 courses in 5 weeks. Neoadjuvant chemotherapy include single drug therapy: capecitabine (CAP, 1250 mg/m^2, BID) or double drug therapy: oxaliplatin combined with capecitabine (CapeOX, oxaliplatin 130 mg/m^2, day 1, capecitabine 1000mg/ m^2, day 1 ~ 14, then rest for 7 days, repeated every 3 weeks) or three-drug therapy (mFOLFOX6, oxaliplatin 85 mg/ m^2 intravenous infusion for 2 hours, leucovorin calcium 400 mg/m^2 intravenous infusion for 2 hours, 5-FU (fluorouracil) 400 mg/m^2 intravenous infusion for 1 day, Then 1200 mg/ m^2/d×2 days of continuous intravenous infusion with a total of 2400mg/m^2 for 46 ~ 48 hours, repeated every 2 weeks.

Abdominal and pelvic MRI and contrast enhanced CT will be routinely performed 6 to 8 weeks after neoadjuvant therapy to confirm the extent of tumor regression without new-found distant metastasis. Those whose clinical stage after neoadjuvant therapy changes from T4 to T3 will be seen as eligible in this study.

➤ **Surgical treatment**

● Preoperative preparation

- 1) Patients older than 60 years old or having a smoking history for over 10 years will receive lung ventilation training and atomization treatment for 3 days
- 2) Intestinal preparation will be done with oral cathartic medications 12-24 hours before surgery
- 3) Prophylactic antibiotics will be given once anesthesia is begun, the second antibiotics will be given if the operation lasts for over 3 hours

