7) 3-year tumor-free survival (month): The time from operation to confirmation of tumor's local recurrence or distant metastasis. The end point of the patient lost to follow-up is the date of loss. 30 days is defined as one month

8) 3-year overall survival (month): The time from operation to death. The end point of the patient lost to follow-up is the date of loss. 30 days is defined as one month

9) Stoma closure time (months since operation). Anal function is assessed by Wexner scale 3 months and 12 months after stoma closure, respectively.

**Table 3.** Wexner score assessing anal function

Type of Incontinence	Frequency				
	Never	Rarely	Sometimes	Usually	Always
Solid	0	1	2	3	4
Liquid	0	1	2	3	4
Gas	0	1	2	3	4
Wear Pad	0	1	2	3	4
Lifestyle altered	0	1	2	3	4

Never - 0

Rarely - Less than once a month

Sometimes - Less than once a week or once a month

Usually - Once a day or once a week

Always - Once a day or more

Score: 0 Perfect; 20 Complete Incontinence

(As to possible risks and benefits of participating in this trial, see details in the *informed consent document*.)

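### Postoperative Wexner scores are compared between non-randomised groups by unadjusted tests, although eligibility already implies a preoperative Wexner score that could be used as a covariate

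*Combined protocol and SAP*

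**What the plan says.** **Baseline.** Exclusion criterion 3 removes "Patients with poor anal function preoperatively (Wexner score" of 10 or more). Enrolled patients therefore have preoperative values from 0 to 9. The preoperative work-up under Treatment does not list a Wexner assessment. The one questionnaire it names is the IIEF-5, for men: "All male patients will be routinely asked to fill" it in.

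**Outcome.** Follow-up item 9 states: "Anal function is assessed by Wexner scale 3 months and 12 months after stoma closure, respectively". The scale runs from 0 to 20. It is not among the Primary outcomes, but the Objective includes postoperative functional outcomes.

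**Group formation.** Methodology describes the design as "Prospective, Non-randomized, Interventional, Controlled". Under Treatment, the last item of preoperative preparation reads: "If the patient refuses to accept the novel approach before surgery, they will be directly enrolled in the traditional group". Patients who accept either approach are assigned during surgery. They enter the experimental group "If the distal rectal transection cannot be done more than 1cm from the lower edge of the tumor", and the traditional group otherwise.

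**Analysis.** For quantitative data the Statistics section says that the t "test and Mann-Whitney *U* test were used for quantitative data between groups". Its other methods are chi-square or Fisher's exact test for qualitative data, and "survival distributions were analyzed by log-rank test". No covariate, change score, regression, propensity score, matching or stratification appears anywhere in the document.

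**The concern.** A preoperative value on the outcome's own scale is needed to screen each patient and then plays no part in the analysis. In a randomised trial that would cost only precision. Here no step in forming the groups balances preoperative continence. A t or Mann-Whitney test on the postoperative score cannot separate a difference that was present before surgery from an effect of the approach. The protocol aims to show advantages of the new approach and counts function among the outcomes that bear on them, so a carried-over baseline difference could be read as better or worse anal function with that approach.

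**Working it through.** **Inputs from the document.** 100 experimental and at least 100 control patients (Sample size); unadjusted tests (Statistics); enrolled baseline Wexner 0 to 9 (Exclusion criteria).

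**Assumed inputs.** The document gives no alpha, power, effect size, Wexner SD or correlation. I take two-sided 5%, 100 per group, correlation ρ between baseline and follow-up of 0.2 to 0.5, equal SDs at both times, and a systematic baseline difference of D standard deviations. There is no planned power figure to reproduce.

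**1. Bias of the unadjusted comparison.** The within-group slope in SD units is ρ, so the bias is b = ρ × D. The standard error of the unadjusted difference is √(2/100) = 0.1414 SD. With no true effect, the false-positive rate is Φ(−1.96 + b/SE) + Φ(−1.96 − b/SE).

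| D | ρ | b (SD) | b/SE | False-positive rate |
|---|---|---|---|---|
| 0 | any | 0 | 0 | 5% |
| 0.2 | 0.3 | 0.06 | 0.42 | 7.1% |
| 0.2 | 0.5 | 0.10 | 0.71 | 10.9% |
| 0.5 | 0.3 | 0.15 | 1.06 | about 19% |
| 0.5 | 0.5 | 0.25 | 1.77 | 42.4% |

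The D = 0.5 rows show how the effect grows. Nothing in the document says a gap of that size will occur.

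**2. Precision with no baseline gap.** Adjustment multiplies the variance by 1 − ρ². At ρ = 0.5 that is 0.75, which cuts the standard error by 13.4%. For an assumed standardised effect of 0.4 (noncentral t), unadjusted power is 80.4%. Adjusted power is 81.9%, 83.9%, 86.7% and 90.1% at ρ = 0.2, 0.3, 0.4 and 0.5.

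**3. Precision with a baseline gap.** The groups now differ on the covariate, which inflates the adjusted variance by about 1 + D²/4. The total factor is (1 − ρ²)(1 + D²/4). Power for the same effect, against 80.4% unadjusted:

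| D | ρ = 0.2 | ρ = 0.3 | ρ = 0.4 | ρ = 0.5 |
|---|---|---|---|---|
| 0.5 | 79.6% | about 82% | about 85% | about 88% |
| 0.8 | 76.0% | 78.2% | about 81% | about 85% |

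Adjustment breaks even where (1 − ρ²)(1 + D²/4) = 1. For D = 0.5 this is ρ = √(1 − 1/1.0625) = 0.24. For D = 0.8 it is ρ = √(1 − 1/1.16) = 0.37. Below those values adjustment costs some power while still removing the bias in step 1.

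**The case against.** **Imbalance is not shown.** Neither refusal nor stapler reach is a continence criterion. A reader might infer that the groups will differ at baseline and that the functional result is therefore biased. The document supports only the weaker statement: nothing prevents such a difference, and nothing in the analysis would remove it. This stands as a limit on the claim.

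**The sizes are assumed.** They are. The 0 to 9 restriction may also limit both the gap and the correlation, and at ρ of 0.2 to 0.3 with no gap the power gain is only about 1.5 to 3.5 points. The number analysed may fall below 100 per group, because the score is taken only after stoma closure and the withdrawal criteria remove some patients. This is why precision is not the main argument.

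**Adjustment is not free.** It is tempting to say the covariate can only help. Step 3 shows otherwise: with a large gap and a low correlation, a few points of power are lost. The bias argument and the full precision gain cannot both be claimed, since one needs a gap and the other assumes none.

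**The score may not be recorded.** The criterion implies a preoperative score, but no section says that a number is kept. It cannot be assumed that the data are already in hand.

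**One covariate is too narrow.** Allocation depends on patient choice and on how far the stapler can reach, so confounding through anatomy or tumour position would remain. This limits what the adjusted result can be called. It is not a reason to leave out the preoperative value of the outcome itself.

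**Wexner is not primary.** True, and no primary result changes. Function is still part of the Objective.

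**Conclusion.** The point holds as a recommended improvement to a non-primary functional analysis. Its main ground is bias: under the assumptions stated, a modest 0.2 SD baseline difference takes the false-positive rate from 5% to about 7% (ρ = 0.3) or 11% (ρ = 0.5). The direction and actual size of any imbalance are unknown. The precision effect is secondary and can go either way: from 80.4% power up to 81.9–90.1% with no gap, but down to 76.0% or 78.2% with a 0.8 SD gap at ρ = 0.2 or 0.3. A reader might also infer that adjusting for the preoperative score makes the functional comparison unconfounded. The allocation rules do not support that, because adjustment removes only the part that runs through baseline continence.

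**What to change.** 1. In the preoperative assessments under Treatment, state that the screening Wexner score is recorded as a number for every patient.
2. In Statistics, make the main comparison at 3 and at 12 months after stoma closure a regression of the postoperative Wexner score on group and preoperative Wexner score. Use robust or bootstrap standard errors, or an ordinal model if the score is skewed, and write the rule for choosing before the outcome data are examined.
3. Report the adjusted group difference with a 95% CI (or the ordinal model's group effect with its CI). Keep the Mann-Whitney test as a sensitivity analysis.
4. State that this adjusts for baseline continence only, and do not describe the result as fully adjusted.

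**Cost.** A short addition to Statistics and one recorded value per patient at screening, with no extra patients. If the number was not kept for patients already enrolled (the study start date is given as December 2020), it would have to be retrieved from screening records or reported as missing. The statistical downside is the possible small loss of precision when the baseline gap is large and the correlation low.
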